## STUDY DESIGN

This is a placebo-controlled, ascending treatment crossover design trial with washout periods of at least one week.

**Primary objective:** Evaluate the effect of single oral administration of naringenin at four escalating doses on safety and tolerability in healthy volunteers.

**Secondary objective:** Evaluate the pharmacokinetics of naringenin at low (150 mg) and high (600 mg) doses to test if changes in serum concentrations are proportional to the dose, by assessing naringenin drug exposure ( $AUC_{0-24}$ ).

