### Randomization Procedure and Blinding

Each subject in the cohorts will be randomly assigned one of the relevant treatment sequences in order of enrollment. Treatment sequence assignments will be balanced so that each sequential block will have unique treatment sequences. As an example, the first three enrolled subjects in each cohort will be randomly assigned to one of three distinct treatment sequences, as will enrollees 4-6 and 7-9. As a result, three of the nine subjects in each cohort will be randomly assigned to each of the three treatment sequences. The randomization scheme will be prepared by [name] under the supervision of [name]. Except for the pharmacist who will prepare and dispense the capsules, all study staff and the investigators will be blinded to the randomization.

Table 2. Schedule of Assessments

	Screening	Visit 1a	Visit 1b	Visit 2a	Visit 2b	Visit 3a	Visit 3b
Consent	x						
Height	x						
Weight	x	x		x		x	
Blood Pressure/Pulse/Temperature	x	x		x		x	
Medical History Questionnaire	x						
Pregnancy Test (Urine)*	x						
Concomitant Medications	x						
Chemistry Panel/CBC	x						
Adverse Events		x	x	x	x	x	x
Plasma naringenin			x			x	x
Chemistry Panel/CBC (0 hr)**		x		x		x	
Chemistry Panel/CBC (24 hrs later)**			x		x		x
Naringenin Administration		x		x		x	
IV Placement		x					
Blood Collection at 0, 2, 3, 3.5, 4, 4.5, 6, 8, and 12 hours		x					

\* Women of Child bearing potential

\*\* For Cohort 2 only BUN, AST, and Bilirubin added to Chem 15 panel

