## STUDY PROCEDURES

### Clinical Chemistry

**Safety Assessments:** Blood will be drawn at time 0 (before ingestion of each dose of naringenin, or placebo) and the subject will return 24 hours later (the next morning) for a repeat chemistry panel and CBC to assess safety of naringenin. Four ml of blood will be drawn for each of these tests. An additional 2 ml will be drawn with the 24 hour specimen to measure serum naringenin concentrations.

- Chemistry 15 Panel will be performed according to standard procedures for blood draws and the relevant chemistry panel.
- Comprehensive Blood Count (CBC) will be performed according to standard procedures.

**Pharmacokinetic Testing:** To evaluate the pharmacokinetics of naringenin, blood (two ml) will be drawn prior to administration of naringenin and at 2, 3, 3.5, 4, 4.5, 6, 8, 12 and 24 hours post-dose of 150 and 600 mg naringenin, and at four hours after the 300 and 900 mg doses. The serum will be separated from the blood, frozen and sent on dry ice to University of Tennessee for measurement of serum naringenin concentrations. This time course stretches over what is estimated to be five half-lives so a complete pharmacokinetic profile can be described including the maximal concentration achieved, time to peak, half-life, area under the curve, and apparent oral clearance ( $C_{max}$ ,  $T_{max}$ ,  $T_{1/2}$ ,  $AUC_{0-24hr}$  and  $Clearance_{oral}$  respectively).

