## **STATISTICAL CONSIDERATIONS**

As comparative efficacy of the doses of the extract is not the primary issue in this protocol, power to detect efficacious effects is not specifically evaluated to justify sample sizes. A sample of 18 subjects (three subjects in each of three treatment sequences in each of two cohorts) will be enrolled in the ascending single dose evaluation. Thus, all nine subjects in Cohort 1 will receive the placebo and both 150 and 300 mg doses of the extract; similarly all 9 subjects in Cohort 2 will receive the placebo and both 600 and 900 mg doses of the extract. Before the next cohort is commenced, subjects in the preceding cohort must have received all three treatments and the safety and tolerability data must have been assessed showing tolerance to the doses of naringenin. Based on the pharmacokinetic study done in humans, the sample size (n=6, at each dose) is sufficient to provide a pharmacokinetic profile of naringenin in serum.

The primary outcome will be to determine the effect of the naringenin extract on safety and tolerability based on clinical and biochemical assessment.

The secondary outcome will be to determine the pharmacokinetics of naringenin at the 150 mg and 600 mg doses. Serum concentrations of naringenin will be obtained to assess drug exposure.

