### Stopping Rules

Dosing within a cohort will be stopped and further dosing will be halted until un-blinded safety information can be reviewed in the event that:

- A death occurs
- Two or more subjects experience the same SAE following administration of study product.
- Two or more subjects in each cohort experience the same severe study product-related AE following administration of study product
- Based on AEs, laboratory findings, or clinical findings the Investigator determines that review of pertinent safety information is required.

Dosing may only resume if, after review of safety information, both the Investigator and IRB agree that it is safe to proceed.

**Pharmacokinetics of naringenin extract.** Pharmacokinetics of orally administered naringenin will be analyzed using a non-compartmental model. The maximal concentration ( $C_{max}$ ), time to peak ( $T_{max}$ ), half-life ( $T_{1/2}$ ), area under the serum concentration versus time curve ( $AUC_{0-24hr}$ ) and apparent oral clearance ( $Clearance_{oral} = Dose/AUC_{0-24hr}$ ) for each subject will be determined and the means for subjects given 150 mg and 600 mg doses will be calculated. Pairwise comparisons of 150 mg, 600 mg and placebo will be tested with a linear model for each of the parameters ( $C_{max}$ ,  $T_{max}$ ,  $T_{1/2}$ ,  $AUC_{0-24hr}$  and  $Clearance_{oral}$ ) across all time points. All analyses will use SAS Version 9.4 software (SAS Institute Inc., Cary NC).

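### The pharmacokinetic comparison puts placebo in the model and runs over time points that the parameters do not have; with no scale or variance structure named, the default fit would be miscalibrated

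*Combined protocol and SAP*

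**What the plan says.** The analysis is in Statistical Considerations, in the paragraph on the pharmacokinetics of naringenin extract, which sits under Stopping Rules.

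- Derivation: "Pharmacokinetics of orally administered naringenin will be analyzed using a non-compartmental model". Cmax, Tmax, T1/2, AUC0-24 and clearance (dose divided by AUC0-24) "for each subject will be determined and the means for subjects given 150 mg and 600 mg doses will be calculated".
- Comparison: "Pairwise comparisons of 150 mg, 600 mg and placebo will be tested with a linear model for each of the parameters". After the list of five parameters the sentence ends: "across all time points. All analyses will use SAS Version 9.4 software".
- Sampling, under Clinical Chemistry: a pre-dose sample and samples "at 2, 3, 3.5, 4, 4.5, 6, 8, 12 and 24 hours post-dose of 150 and 600 mg naringenin", so ten concentrations per profile.
- Aim, under Study Design: "to test if changes in serum concentrations are proportional to the dose", assessed by AUC0-24.
- Size, under Statistical Considerations: "the sample size (n=6, at each dose) is sufficient to provide a pharmacokinetic profile of naringenin in serum".

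The plan does not say whether parameters are analysed raw or logged, whether means are arithmetic or geometric, or whether the dose groups share one error variance. It does not explicitly plan confidence intervals for these comparisons.

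**The concern.** This is the only planned analysis of the secondary outcome. It has three weaknesses.

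1. The model is to run over time points, but its outcome variables have none. The ten concentrations have already been collapsed into one number per parameter per subject.
2. Placebo is a third group. Its AUC and Cmax are near zero with almost no spread. Its half-life cannot be estimated, its Tmax means nothing, and its clearance is a dose of zero divided by an AUC of about zero. A group with almost no variance lowers a pooled error estimate and so shortens the error bars on the comparison that matters, 600 against 150 mg.
3. The doses differ fourfold and no scale is named. If exposure is proportional to dose and relative variability is constant, the SD of AUC and Cmax at 600 mg is about four times that at 150 mg, which a raw-scale model with one variance ignores.

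At stake is whether the reported comparison of exposure between the two doses has the error rate it claims, and whether it answers the dose-proportionality question.

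**Working it through.** **The plan's own figure.** The Visit 1 description places the full profile at that visit. By Table 1, sequences 1 and 2 receive 150 mg then, and sequences 4 and 5 receive 600 mg. With 3 subjects per sequence ("three of the nine subjects in each cohort will be randomly assigned to each of the three treatment sequences"), that is 2 x 3 = 6 per dose, which reproduces n=6. Sequences 3 and 6 give 2 x 3 = 6 placebo profiles at Visit 1.

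**Variability.** The documents give no SD for AUC or Cmax. The only variability figure is the half-life of 2.31 ± 0.4 h (Rationale for Naringenin Dose), a CV of 0.4/2.31 = 17% if ± is an SD. I assume CVs of 17% to 60%.

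**Effect of placebo on the pooled error.** Let vA and vB be the sample variances at 150 and 600 mg, with placebo at zero variance and n=6 per group.

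- Three-group pooled variance: 5(vA + vB)/15 = (vA + vB)/3.
- Two-group pooled variance: 5(vA + vB)/10 = (vA + vB)/2.
- Ratio of standard errors: sqrt(2/3) = 0.816.
- The three-group test uses the critical value t(15) = 2.131. It therefore rejects when the proper 10-df statistic exceeds 2.131 x 0.816 = 1.740.
- For normal data with no dose difference, P(|t10| > 1.740) = 0.112, against a nominal 0.05.

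**Simulation.** Log-normal values, n=6 per group, placebo 0, 40,000 trials per setting (Monte Carlo error below 0.4 points). Coverage is for a nominal 95% interval when the true mean ratio is 4. Rejection is for a nominal 5% test of 600 against 150 mg when the means are equal.

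| CV | Coverage, raw, three groups | Coverage, raw, placebo dropped | Coverage, log scale, two doses | Rejection under no difference, raw, three groups | Rejection under no difference, raw, placebo dropped |
|---|---|---|---|---|---|
| 17% | 86.4% | 92.8% | 95.2% | 11.4% | 5.1% |
| 30% | 85.8% | 92.3% | 94.9% | 11.0% | 4.7% |
| 40% | 85.3% | 91.8% | 95.2% | 11.0% | 4.7% |
| 50% | 84.2% | 90.8% | 94.9% | 10.9% | 4.5% |
| 60% | 83.7% | 90.1% | 95.1% | 10.3% | 4.0% |

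If all nine subjects per dose were profiled, taking n=9 in each group, three-group coverage would be 87.2%, 86.7% and 85.6% at CV 17%, 30% and 50%, so the conclusion is the same.

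**Which parameters are affected.** The unequal-spread argument applies to AUC and Cmax. Under linear kinetics clearance, T1/2 and Tmax do not change with dose; with placebo left out, raw-scale coverage for such a parameter is about 95-96%. For clearance and T1/2 the trouble comes through placebo. If placebo values are set to missing, the group drops out and little harm follows. If they are entered as 0, the 10-11% error rate applies.

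**Tmax.** It can take only the scheduled sampling times (2 to 24 h), so a normal-theory comparison of means suits it poorly.

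**The case against.** The strongest reply is that the plan is brief rather than wrong. A log-scale model is a linear model, and so is one with unequal variances; nothing in the text rules out either. A reader might infer that the plan commits to untransformed values with one error variance. It does not: it is silent on both, and the figures above are conditional on the default fit. That part of the objection stands.

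A reader might also infer that type I error is lost altogether. Entering each subject's value ten times as independent rows would inflate t by sqrt(177/15) = 3.44 for three groups of 6, and a nominal 5% test would reject about 57% of the time. But the plan describes no such stacked data set, and the sentence before it derives parameters subject by subject. The likelier intent is that the parameters draw on the whole sampling course. The clause is undefined; it is not evidence of a 57% error rate.

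Third, the test of equality between doses rarely changes. With a true fourfold difference it rejects in 98-100% of trials in the three-group raw fit, 90-100% in the two-group raw fit and 97-100% on the log scale. This also stands, but equality is not the question in Study Design. A 600:150 mg AUC ratio has to be set against the dose ratio of 600/150 = 4, and there the accuracy of the interval matters. The clearance comparison bears on proportionality, since clearance is dose over AUC, but the plan does not present it as that test and includes placebo in it.

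Finally, pharmacokinetics is secondary, and the move to Cohort 2 rests on safety and tolerability data. That limits the severity.

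**Conclusion.** The point holds in a limited form. Two features are defects as written: the time-point clause, which has no meaning for parameters with one value per subject, and placebo as a group in models of parameters it cannot supply. A third is an omission: no scale or variance structure is stated.

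Under the default raw-scale, pooled, three-group fit, a nominal 95% interval for 600 minus 150 mg covers about 84-86%, and a nominal 5% test rejects about 10-11% of the time under no difference. Dropping placebo brings these to 90-93% and 4-5%, so placebo is the larger cause. This rests on assumed log-normal values, constant CV of 17-60%, 6 per group and placebo at zero, and for the coverage figures on dose-proportional exposure. Spread rising with dose is itself an assumption, reasonable for AUC and Cmax.

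It would go too far to conclude that the intervals and p-values for all five parameters are wrong. No intervals are explicitly planned, and clearance and T1/2 are affected mainly through placebo. The point should be fixed, but as a secondary-outcome matter it does not threaten the trial's primary purpose.

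**What to change.** Replace the comparison sentence with text to this effect:

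- Each subject contributes one value per parameter. Delete the time-point clause, or keep it only for a descriptive concentration-time plot.
- Placebo concentrations are listed and not entered in the parameter models.
- AUC0-24, Cmax, T1/2 and clearance are compared between 150 and 600 mg on the log scale and reported as geometric means and a 600:150 mg ratio with its confidence interval.
- AUC0-24 and Cmax are dose-normalised and the ratio judged against 1, or left as they are and the ratio judged against 4, so that the analysis answers the dose-proportionality objective.
- Tmax is reported as median and range, with a rank-based comparison.
- The number of profiles per dose is stated (6 by the Visit 1 schedule).

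The cost is wording only: same samples, same data, same software. The result should be presented as an estimate. With 6 per dose, the 90% interval for a geometric mean ratio runs from the estimate divided by, to the estimate multiplied by, exp(1.812 x s x sqrt(2/6)), where s = sqrt(ln(1 + CV²)). That factor is 1.36 at an assumed CV of 30% and 1.64 at 50%.

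### Dose proportionality rests on a 150 v 600 mg contrast that cannot be separated from cohort, and the 4-hour samples after 300 and 900 mg, which could check it within subject, enter no analysis

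*Combined protocol and SAP*

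**What the plan says.** The secondary objective under Study Design is "to test if changes in serum concentrations are proportional to the dose, by assessing naringenin drug exposure" as AUC0-24, at 150 mg (low) and 600 mg (high).

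Statistical Considerations and Table 1 fix who receives what. In the first cohort, "all nine subjects in Cohort 1 will receive the placebo and both 150 and 300 mg doses of the extract"; in the second, "similarly all 9 subjects in Cohort 2 will receive the placebo and both 600 and 900 mg doses of the extract". Cohorts run in series with a gap of up to four weeks (Safety and tolerability). Randomisation is to sequence within cohort, not to cohort (Randomization Procedure and Blinding).

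The paragraph on pharmacokinetics of naringenin extract, placed under Stopping Rules, gives the analysis: non-compartmental parameters, means at 150 and 600 mg, and then "Pairwise comparisons of 150 mg, 600 mg and placebo will be tested with a linear model for each of the parameters". It names neither 300 nor 900 mg and mentions no log scale, subject effect or cohort term. Apparent oral clearance is defined as dose divided by AUC0-24.

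Pharmacokinetic Testing, under Clinical Chemistry, orders full profiles after 150 and 600 mg, including a 4-hour point, "and at four hours after the 300 and 900 mg doses". The visit descriptions organise the same sampling by visit: a full profile at Visit 1, a 4-hour draw at Visit 3a and no naringenin sample at Visit 2.

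**The concern.** The only active-dose comparison in the pharmacokinetic analysis sets one group of people against another, recruited at a different time and not randomised between the two dose ranges. If the cohorts differ in absorption or clearance, by chance or through recruitment, that difference is indistinguishable from a departure from proportionality. It could create an apparent departure or hide a real one. Fitting a cohort term does not help with these two doses alone, because dose and cohort are then the same variable.

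Each subject also takes a second active dose, and blood is ordered four hours after it. That sample can be matched to the 4-hour point of a 150 or 600 mg profile in the same person. It is the only check in the trial that does not depend on the cohorts being alike, and no use for it is stated.

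A related weakness is that a pairwise test of raw AUC or Cmax at 150 v 600 mg tests equality, not proportionality. Of the exposure measures listed, only clearance is dose-normalised.

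**Working it through.** **1. The plan's own counts.** Six sequences of three give 18 subjects, as stated. The full profile is at Visit 1, when two of the three sequences in each cohort take the lower dose: 2 × 3 = 6. This matches the stated n=6 at each dose.

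**2. Effect of a cohort difference.** The slope from two doses is ln(exposure ratio) / ln(600/150), with ln 4 = 1.386. A true cohort ratio g therefore shifts it by ln g / ln 4:
- g = 1.2: 0.13
- g = 1.5: 0.405/1.386 = 0.29
- g = 2: 0.50

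**3. How many within-subject pairs exist.** Set Table 1 against the visit descriptions:
- Sequences 1 and 4 take the lower dose at Visit 1 (profile) and the higher at Visit 3 (4-hour draw), so both are sampled.
- Sequences 2 and 5 take the higher dose at Visit 2, where nothing is drawn for naringenin. Their Visit 3a draw follows placebo, so only the lower dose is sampled.
- Sequences 3 and 6 have placebo at Visit 1 and the lower dose at Visit 2, so only the higher dose is sampled.

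By visit there are three pairs per cohort. By the dose-based wording of Pharmacokinetic Testing there are nine.

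**4. Precision.** The documents give no CV for AUC or concentration. Assume 50% between and 25% within subject, and equal variance for 4-hour concentration and AUC. On the log scale, variance = ln(1 + CV²), so σb² = 0.2231, σw² = 0.0606 and the total v = 0.2838 (SD 0.533).

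*Planned contrast*, 90% half-width = t × 0.533 × √(2/n) / 1.386:
- n=6: 1.812 × 0.3076 / 1.386 = 0.40
- n=9: 1.746 × 0.2511 / 1.386 = 0.32

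*Four-dose model with a cohort term.* The slope uses only the within-cohort dose steps, ln 2 and ln 1.5: (ln 2)² + (ln 1.5)² = 0.4805 + 0.1644 = 0.6449.
- Nine pairs per cohort: variance of the mean log difference = 2σw²/9 = 0.01347; slope SE = √(0.01347/0.6449) = 0.1445; half-width = 1.746 × 0.1445 = 0.25.
- Visit-listed draws (three pairs, three lower only, three higher only per cohort): variance = 2/(3/σw² + 3/v) = 2/(49.5 + 10.6) = 0.0333; slope SE = √(0.0333/0.6449) = 0.227; half-width = 1.746 × 0.227 = 0.40.

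Both use 16 degrees of freedom, which is favourable to the visit-listed case because it has only six pairs in all. Over CVs of 30–70% between and 15–35% within subject, the ranges are 0.15–0.35 and 0.24–0.55.

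**5. What the cohort term does.** Without it, the half-widths fall to 0.20 (nine pairs) and 0.26 (visit-listed), but a 1.5-fold cohort difference still biases the slope by 0.12 and 0.19 respectively. With it, that bias is zero.

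**The case against.** The objective is narrow. It names two doses and AUC0-24, and a single 4-hour level cannot supply AUC0-24. The crossover mainly serves the safety comparison, where placebo and both doses are compared within subject. The clearance comparison is already a dose-normalised AUC comparison, because it is its reciprocal. All of this stands. It limits the 4-hour analysis to a supporting role, but it does not remove the aliasing of 150 v 600 mg with cohort or give the extra samples a use.

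A reader might infer that the unused samples would halve the uncertainty, from 0.40 to 0.20. The documents do not support that. The 0.20 needs the cohort term left out, which keeps part of the confounding. It also needs dose-based sampling, under which the planned contrast would itself have nine per dose and a half-width of 0.32. On a like-for-like basis with the cohort term, the comparison is 0.25 against 0.32, or 0.40 against 0.40.

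A reader might also infer that every subject already serves as their own control. By the visit descriptions only three per cohort do. With three pairs the within-subject ratio alone is weak: at an assumed within-subject CV of 30%, its 90% CI around 1 is 0.50–2.01, against 0.77–1.29 with nine pairs.

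**Conclusion.** The concern holds in this form. The sole planned proportionality contrast is between different subjects and inseparable from cohort, so a 1.5-fold cohort difference moves the apparent slope by 0.29, and the 300 and 900 mg samples that could check it are not analysed. The main benefit of using them is a slope that does not depend on the cohorts being alike. Precision improves if nine pairs per cohort are sampled (0.25 v 0.32) and is about unchanged with the visit-listed draws (0.40 v 0.40).

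The 0.29 is arithmetic and needs no CV. The half-widths rest on assumed CVs and on equal variance of 4-hour concentration and AUC. The within-cohort slope also spans only 2-fold and 1.5-fold dose steps and assumes one slope across both. Every sequence gives the lower dose first, so a period effect would enter the ratios. The text does not support calling the crossover wasted, or treating 4-hour concentration as a substitute for AUC0-24. This is a worthwhile correction to a secondary analysis.

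**What to change.** Add to the pharmacokinetics paragraph:

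> *As supportive evidence, log 4-hour concentration at 150, 300, 600 and 900 mg will be regressed on log dose with a random subject effect and a fixed cohort term. The slope and its 90% CI will be reported, with the within-subject ratios 300/150 and 900/600.*

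Keep the 150 v 600 mg clearance comparison (Dose/AUC0-24) as the dose-normalised comparison of exposure, and label it a between-cohort contrast.

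Reconcile the sampling described by visit (Visits 1 to 3b and Table 2) with that described by dose (Pharmacokinetic Testing), because this decides whether there are three or nine pairs per cohort.

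The cost is a few lines of text, with no samples beyond those Pharmacokinetic Testing already orders. If the visit lists are what is actually followed, reaching nine pairs would mean adding draws to those lists. The drawback is that a 4-hour level also moves if Tmax shifts with dose, which is why the analysis is labelled supportive. The text should be fixed before unblinding so that the analysis is not post hoc.
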